#### **7.2.9.1. 36-Month Follow-Up Dual-energy X-ray absorptiometry (DXA)**

If PCP thinks it is clinically relevant for the participant to have a DXA scan after the 36-months, the Research staff will take the participant to have the DXA scan at the Penn State Hershey Breast Center. The DXA scan should not take more than 30 minutes.

If the participant has received a DXA scan within 1 years of their 36-month visit date, the research staff person will request a copy of the DXA report either from the participant or the participant's PCP.

#### **7.2.10 Quarterly Newsletters**

As a part of our retention strategy, all of the participants will be mailed a newsletter every 3 months. These newsletters will be used to promote ongoing support and participation and to provide ongoing information related to the research study. The content of the newsletter may include study updates, information about study staff, healthy living tips, a crossword puzzle or similar game, or recipes. In addition to the previously mentioned content, the intervention arm's newsletter may contain updates specific to active exercise sites, DVD updates, or exercise updates.

#### **7.3 Duration of Participation**

All participants will be in the study for 36 months. Group leaders will be in the study for 36 months or until the last participant is enrolled, whichever date comes first. Community members will be in the study until the last participant is enrolled and the study ends. Spanish Speaking Interview Members will be in the study for a one-time phone interview.

## **8.0 Subject Numbers and Statistical Plan**

### **8.1 Number of Subjects**

#### Participants

For the study-wide enrollment (across all 3 institutions) we will aim to enroll 1130 participants. We anticipate about 15% of participants will drop or be lost to follow up or die. We will need a total of 960 to complete the study.

At Penn State, we will aim to enroll 501 participants to the study. We anticipate that about 15% of participants will drop out or be lost to follow up or die. We will need a total of 425 participants to complete the study.

#### Group Leaders

We will enroll about 350 Group leaders into the study across all 3 institutions. At Penn State, we will enroll approximately 125 Group Leaders.

#### Community Members

We will enroll up to 250 community members.

Spanish Speaking Interview Members\_We will enroll up to 75 subjects.

### **8.2 Sample size determination**

In order to have 95% statistical power to detect a 6% difference in the composite outcome measure of SFRI (including FF) between groups at 36 months follow-up, we will enroll 500 subjects at baseline. We assume a Type 1 error rate (alpha) of 5% (.05), statistical power of 95% (.95), and a two-tailed log-rank test for the time until SFRI (including FF), which allows us to detect significant differences in either direction. We estimate that 15% of subjects will be lost to follow-up at 36 months, as losses to follow-up in studies of older adults tend to be lower (37). Also, for subjects lost to follow-up, we will conduct an electronic health record search, to measure the incidence of FF/SFRI. The study is over-powered for the main outcome measure (SFRI, including FF), in order to (1) provide the possibility of seeing an impact on FF, the most clinically meaningful measure and (2) insuring, given the amount of money spent on the study, that it is powered to observe a clinically meaningful difference even if several of our assumptions are not met.

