## **7.0 Study Design and Procedures**

### **7.1 Study Design**

We propose a 36-month multi-center randomized effectiveness trial to compare the impact of an Enhanced Usual Care (Control) intervention, with Exercise Coaching (Exercise), on FF/SFRI in patients with a previous fragility fracture (FF). We will also examine the impact of the intervention on several secondary outcomes like: loneliness, physical function, and bone strength. We will do this by following a Pragmatic trial design: 1) limiting exclusions to increase representativeness, 2) limiting research contacts and 3) limiting measures to those practicable for use in usual care.

The intervention will be held in churches, community centers, and senior residential facilities. We will work with the exercise sites and RSVP and send mailings to recruit up to 125 individuals to serve as the Group leaders at each site location. They will be trained on the exercises and leadership roles to help lead the group. We will ask them to come at least once per week, so the time commitment is minimal.

We will be recruiting approximately 500 patients who have suffered a FF and will randomly assign them to one of two conditions: (A) Control Group – Enhanced Usual Care and (B) Intervention Group – Enhanced usual care plus Exercise coaching that includes in-person and phone coach contacts to encourage and support strength, balance and walking activities.

We will be recruiting up to 250 people that are members of the community that would like to participate in our exercise program. These eligible community members will have access to our exercise program up to 3 times a week and can attend whenever best fits their schedule. The recruitment of community members is to supplement the loss of intervention group participants over the 4 year period of the study. It will also provide a way for participants that have completed the study a way to continue exercising with their group if they so choose.

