### **8.3 Statistical methods**

We will conduct the primary analyses on the main outcome measure, SFRI, including FF. Initially, the two randomized groups will be compared qualitatively on important demographic and other baseline variables to ensure successful randomization. For the primary outcome (SFRI, including FF), we will apply intention to treat (ITT) principles with all available data and the covariates of medical center, age, sex, race and ethnicity, smoking status, education, and anti-osteoporotic medication use included in the primary set of analyses (112, 113). If it is determined that the groups, by chance, are significantly different on other covariates, then we will include those covariates in secondary analyses. Of note, while the original proposed study of 2100 subjects was powered to detect a difference in fragility fractures, the modified sample size of 1130 will be powered only to detect a difference in serious fall-related injuries, of which fragility fracture is only one type. As the rate of fragility fracture is lower than the rate of serious fall-related injury, the study is no longer powered to detect a difference in fragility fracture, yet is powered to detect a difference in serious fall-related injury.

Power Estimates (assuming 15% lost to follow-up, 960 remaining at 3 years).

	Control rate	Intervention Rate	Relative Risk Reduction	Number Needed To Treat	Power
Serious Fall-related injury (BASE)	13%	7%	46%	17	87%
● Scenario 2 (smaller effect)	13%	8%	38%	20	71%
● Scenario 3 (lower rate of FF/SFRI)	12%	6%	50%	17	90%
● Scenario 4 (smaller effect + lower rate of FF/SFRI)	12%	8%	33%	25	54%
Fragility Fracture alone	7%	4%	43%	33	53%

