**Sample Size Calculations.** In order to have 95% statistical power to detect a 6% difference in the composite outcome measure of FF/SFRI between groups at 36 months follow-up, we had planned to enroll 2100 subjects at baseline. Since the original application and after extensive discussions with PCORI in response to a lower-than-expected enrollment rate, we have lowered the recruitment projections to 1130. We assume a Type 1 error rate (alpha) of 5% (.05), statistical power of 87% (.95), and a two-tailed log-rank test for the time until FF/SFRI, which allows us to detect significant differences in either direction. We estimate that 15% of subjects will be lost to follow-up at 36 months (170), as losses to follow-up in studies of older adults tend to be lower. For example, the LIFE study was 2.6 years and had a 97% follow-up rate, with less than 1% dying (4/1635) despite a baseline of 78 (37). Also, for subjects lost to follow-up, we will conduct an electronic health record search, to measure the incidence of FF/SFRI. The study is over-powered for the main outcome measure (SFRI, including FF), in order to 1) provide the possibility of seeing an impact on FF, the most clinically meaningful measure and 2) insuring, given the amount of money spent on the study, that it is powered to observe a clinically meaningful difference even if several of our assumptions are not met (see table above).

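### Section 8.2 gives 95% power for 500 enrolled, but the study-wide plan is 1130 enrolled with 87% power, and the retained over-powered wording is not supported by the plan's own power table

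*Combined protocol and SAP*

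**What the plan says.** Four places in the combined protocol and SAP bear on this.

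- **Section 8.1, Participants:** "For the study-wide enrollment (across all 3 institutions) we will aim to enroll 1130 participants". With 15% loss, 960 are to complete. The Penn State target is 501 enrolled and 425 completing.
- **Section 8.2:** for a 6-point difference at 36 months, "we will enroll 500 subjects at baseline. We assume a Type 1 error rate (alpha) of 5% (.05), statistical power of 95% (.95". The test is "a two-tailed log-rank test for the time until SFRI (including FF"). The section goes on to call the study over-powered for the main outcome. Two reasons are given: to allow a chance of seeing an effect on fragility fracture (FF), and to protect against failed assumptions.
- **Section 8.3:** the power table assumes 960 completers and gives 87% for the base case of 13% v 7%. The text above it says that "the study is no longer powered to detect a difference in fragility fracture". The Sample Size Calculations paragraph below it ties 95% power to the former plan of 2100 and explains the cut to 1130. It then states "statistical power of 87% (.95), and a two-tailed log-rank test for the time until FF/SFRI", and closes by saying that the study is "powered to observe a clinically meaningful difference even if several of our assumptions are not met (see table above").
- **Section 7.1:** "We will be recruiting approximately 500 patients who have suffered a FF", with no mention that this is one site's number.

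**The concern.** Section 8.2 is where a reader looks for the sample size, and it pairs one site's enrolment with a power figure that section 8.3 assigns to the abandoned 2100-subject plan. Section 8.3 then prints two different powers in one phrase.

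The sentence about surviving several failed assumptions is a separate problem. It stands as current text in both sections and is corrected nowhere. In section 8.3 it cites the table as support, although several rows of that table show power well below the base case.

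What is at stake is the design information that readers and funders will take from the plan. Section 12.2 says the results may inform insurance and Medicare coverage decisions. Someone who relies on section 8.2 would believe that the trial has 95% power with room to spare. The plan's own figure is 87%, and it falls quickly if the effect is smaller than hoped.

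**Working it through.** **Inputs.** Two-sided alpha 0.05 and the log-rank test (8.2); 13% v 7% at 36 months (1.1, Aim 1, and the 8.3 table); 1:1 allocation (7.2.6.3); 15% loss (8.1 to 8.3); 1130 enrolled and 960 completers (8.1, 8.3); 500 enrolled (8.2).

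**Formula.** Two-proportion normal approximation with pooled null variance and n completers per arm:

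power = Φ{ [ |p1 − p2|·√n − 1.96·√(2·p̄·(1 − p̄)) ] / √(p1(1 − p1) + p2(1 − p2)) }

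For 13% v 7%, p̄ = 0.10, so √(2 × 0.10 × 0.90) = 0.4243 and 1.96 × 0.4243 = 0.8315. The denominator is √(0.1131 + 0.0651) = 0.4221.

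**Step 1: reproduce the plan's table.** 960 completers give n = 480. For the base case, 0.06 × √480 = 1.3145, and (1.3145 − 0.8315)/0.4221 = 1.144, so power is 87.4%. All rows:

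| Row in 8.3 | Rates | Plan | Recomputed |
|---|---|---|---|
| Base | 13% v 7% | 87% | 87.4% |
| Scenario 2 | 13% v 8% | 71% | 71.5% |
| Scenario 3 | 12% v 6% | 90% | 90.2% |
| Scenario 4 | 12% v 8% | 54% | 54.2% |
| FF alone | 7% v 4% | 53% | 53.1% |

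Every row agrees within one point, so the method is consistent with the plan's.

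**Step 2: apply it to the pairing in 8.2.**

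- 500 enrolled with 15% loss leaves 425 completers, n = 212.5: 0.06 × √212.5 = 0.8746; (0.8746 − 0.8315)/0.4221 = 0.102; power 54%.
- 500 with no loss, n = 250: 0.06 × √250 = 0.9487; (0.9487 − 0.8315)/0.4221 = 0.278; power 61%.

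**Step 3: try log-rank and other variants.** Under exponential survival the hazard ratio is ln 0.93 / ln 0.87 = 0.521. At 425 completers the expected events are 212.5 × 0.20 = 42.5. Schoenfeld's formula gives 56.5% and Freedman's 53.7%. With no loss (50 events) they give 63.5% and 60.5%. Continuity correction and Fisher's exact test give about 48% at 425 completers. Even a one-sided 5% test with no loss reaches only 72%. At 960 completers Freedman gives 87.0% and Schoenfeld 89.1%.

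**Step 4: what 95% would need.** n = (0.8315 + 1.645 × 0.4221)² / 0.06² = 646.8 per arm, or about 1294 completers. Dividing by 0.85 gives about 1522 enrolled. Other variants range from about 1450 to 1600.

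**Step 5: credit the health record search in full.** If outcomes were recovered for every lost subject, 1130 would contribute, n = 565: 0.06 × √565 = 1.4262; (1.4262 − 0.8315)/0.4221 = 1.409; power 92%. Scenario 4 would rise to 61%.

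**Step 6: the former plan.** 2100 × 0.85 = 1785 completers gives 99% for the base case, 80% for Scenario 4 and 79% for FF. The over-powered wording fitted that plan.

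**The case against.** The best reply is that the correct figures are already printed. Section 8.1 gives 1130 study-wide and 501 at Penn State. Section 8.3 gives all five powers, assigns 95% to the 2100 plan in the past tense, and admits that FF is no longer powered. Aim 3 says that most subgroup analyses fall below 80%. This stands, and it limits the point to wording. It does not remove it: section 8.2 is still wrong as written, and the robustness sentence is repeated directly below the table.

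Three stronger readings are tempting, and the documents do not support them.

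- *The trial has 54% power.* A reader might infer this from section 8.2. But 500 is evidently the Penn State share, and no separate Penn State comparison is planned, so 54% is not the power of any planned analysis. It only shows that 500 and 95% cannot belong together. It is also unrelated to the 54% in Scenario 4, which is for 960 completers at 12% v 8%.
- *The table refutes robustness altogether.* It does not. With a lower event rate and the 6-point gap kept, power is 90%, above the base case. The weakness is to a smaller effect. Likewise, a possibility of seeing an FF effect is not a power claim; at 53% it sits awkwardly with section 8.3 but does not flatly contradict it.
- *A null result could not exclude a one-third reduction.* That depends on the observed confidence interval, not on planned power. As an illustration, with 480 per arm and equal observed rates, the 95% interval for the relative risk is 0.71 to 1.41 at 12% and 0.68 to 1.46 at 10%. Both exclude 0.67. At 8% it is 0.65 to 1.54, which does not.

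The planned health record search is also a fair point: 87% is conservative. Full recovery gives 92%, which is still short of 95%.

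**Conclusion.** The point holds as an internal contradiction in the stated sample size and power. The study-wide plan supports 87% power for 13% v 7% at 960 completers, and at most about 92% if no outcome is lost. The 95% in section 8.2 and the .95 in section 8.3 do not apply to the current trial. No standard calculation brings 500 subjects near 95%.

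The claim that the trial is over-powered and withstands several failed assumptions is not supported for a smaller effect: 71% for 13% v 8%, 54% for 12% v 8%, and 53% for FF alone.

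These figures rest on the plan's own event rates, two-sided 5% test, 1:1 allocation and 15% loss. That 500 is the Penn State target is an inference from its match with the 501 in section 8.1; the plan does not say so in section 8.2.

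**What to change.** 1. In section 8.2, state 1130 enrolled study-wide (501 at Penn State), 960 expected completers and 87% power for 13% v 7%. Remove the 95% claim.
2. In the Sample Size Calculations paragraph of section 8.3, delete the bracketed .95 after 87%. Keep 95% only as history of the 2100-subject plan.
3. In section 7.1, label the approximately 500 as the Penn State share.
4. In sections 8.2 and 8.3, replace the over-powered and failed-assumptions sentences with the table's powers: 71% for 13% v 8%, 90% for 12% v 6%, 54% for 12% v 8%, and 53% for FF alone.
5. Do not add a sentence on what a null result would exclude. That should be read from the confidence interval.

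The cost is protocol wording only. Enrolment, randomisation and analysis do not change. The stated power becomes less favourable than section 8.2 now claims.

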### **8.3 Statistical methods**

We will conduct the primary analyses on the main outcome measure, SFRI, including FF. Initially, the two randomized groups will be compared qualitatively on important demographic and other baseline variables to ensure successful randomization. For the primary outcome (SFRI, including FF), we will apply intention to treat (ITT) principles with all available data and the covariates of medical center, age, sex, race and ethnicity, smoking status, education, and anti-osteoporotic medication use included in the primary set of analyses (112, 113). If it is determined that the groups, by chance, are significantly different on other covariates, then we will include those covariates in secondary analyses. Of note, while the original proposed study of 2100 subjects was powered to detect a difference in fragility fractures, the modified sample size of 1130 will be powered only to detect a difference in serious fall-related injuries, of which fragility fracture is only one type. As the rate of fragility fracture is lower than the rate of serious fall-related injury, the study is no longer powered to detect a difference in fragility fracture, yet is powered to detect a difference in serious fall-related injury.

Power Estimates (assuming 15% lost to follow-up, 960 remaining at 3 years).

	Control rate	Intervention Rate	Relative Risk Reduction	Number Needed To Treat	Power
Serious Fall-related injury (BASE)	13%	7%	46%	17	87%
● Scenario 2 (smaller effect)	13%	8%	38%	20	71%
● Scenario 3 (lower rate of FF/SFRI)	12%	6%	50%	17	90%
● Scenario 4 (smaller effect + lower rate of FF/SFRI)	12%	8%	33%	25	54%
Fragility Fracture alone	7%	4%	43%	33	53%

**Sample Size Calculations.** In order to have 95% statistical power to detect a 6% difference in the composite outcome measure of FF/SFRI between groups at 36 months follow-up, we had planned to enroll 2100 subjects at baseline. Since the original application and after extensive discussions with PCORI in response to a lower-than-expected enrollment rate, we have lowered the recruitment projections to 1130. We assume a Type 1 error rate (alpha) of 5% (.05), statistical power of 87% (.95), and a two-tailed log-rank test for the time until FF/SFRI, which allows us to detect significant differences in either direction. We estimate that 15% of subjects will be lost to follow-up at 36 months (170), as losses to follow-up in studies of older adults tend to be lower. For example, the LIFE study was 2.6 years and had a 97% follow-up rate, with less than 1% dying (4/1635) despite a baseline of 78 (37). Also, for subjects lost to follow-up, we will conduct an electronic health record search, to measure the incidence of FF/SFRI. The study is over-powered for the main outcome measure (SFRI, including FF), in order to 1) provide the possibility of seeing an impact on FF, the most clinically meaningful measure and 2) insuring, given the amount of money spent on the study, that it is powered to observe a clinically meaningful difference even if several of our assumptions are not met (see table above).

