### 1.3 Secondary Study Endpoints

**Self-Reported Falls and Fall-Related Injuries:** We will examine the number of falls, and fall-related injuries using two questions from the Behavioral Risk Factor Surveillance System (BRFSS) at baseline, and using the STRIDE questionnaire for all 4-month follow-up assessments (34).

**Self-Reported Health, Physical Function, Fatigue, Pain, Sleep Disturbance, Ability to Participate in Social Roles and Activities, Depression, Anxiety, Loneliness:** We will use 33 self-reported questions to assess key patient centered outcomes that the intervention may improve: self-reported health (1 question), depression (4 questions), anxiety (4 questions), physical function (4 questions), ability to participate in social roles and activities (4 questions), fatigue (4 questions), pain (5 questions), sleep disturbance (4 questions), ability to participate in social roles and activities and loneliness (3 questions). We will use depression, anxiety, fatigue, pain, sleep disturbance and physical function scales from the NIH-supported Patient Reported Outcomes Measurement Information System (PROMIS). We will also use the single-item measure of self-reported health, which is strongly predictive of many health outcomes (37, 38). We will use a 3-item loneliness questionnaire which has high 12-month test-retest reliability ( $r = 0.73$ )(39) and is predictive of future functional decline and death (40). To assess physical function, we will use the 4-item PROMIS measure of physical functioning that includes ability to *walk, do chores, run errands* and *go up and down stairs*, key physical functions. [name], a clinical psychologist and Professor at Penn State with experience in clinical trials to improve anxiety and depression (41-44), will oversee the analysis of these survey results.

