**Height and weight:**

For Group leaders we will collect self-reported height and weight. These will be collected during baseline and at 36 months assessments.

For participants we will use height and weight to calculate Body Mass Index (BMI) using standardized procedures. We will use a portable, calibrated stadiometer and scale with high reliability ( $r = 0.96$ ) (50) as in [name] ongoing study.

**Fear of Falling:** We hypothesize that the intervention will reduce fear of falling as a mediator to increasing physical activity. We will use the 7-item version of the Falls Efficacy Scale International (FES-I), which has high test-retest ( $r = 0.80$ ) reliability and is strongly associated with future falls and depression ( $p < .001$ ) (51).

**Osteoporosis and Other Medications:** At baseline, past osteoporosis medication use will be obtained and, at the 36 month assessments, patients will be asked for their current list of medications.

**30 Second Chair Stand Test:** At baseline and the 36 month follow-up the participants will perform the 30 second chair stand test. This will be used as a measure of functional lower extremity strength.

**30 Second Arm Curl Test:** At baseline and the 36 month follow-up the participants will perform the 30 second arm curl test. This will be used as a measure of functional upper extremity strength.

**Cognition Screener:** Six-item Callahan screener

**Physical Activity Survey:** We will use the NHIS physical activity questions (6 questions) at baseline and 12, 24, and 36 month follow-ups to measure participants' activity level. The survey identifies patients that are sedentary, moderately active, or very active.

**Social domain – caregiver:** We will use two questions from the AARP Caregiver Identification Study, February 2001 at baseline and 36-month follow-up. We will be able to identify whether the patient is a caregiver or not.

**Additional self-reported questions:** We will have participants answer the following 16 questions on chronic conditions, recent healthcare utilization, medical devices, hospital admissions, transportation, health insurance, home care, and nursing home/rehab facility stay.

**Virtual Short Physical Performance Battery (VSPPB):** The vSPPB is a novel self-report measure that uses computer animation to present the physical tasks in the SPPB. We will send 12 questions via email at the Month 36 Visit to all participants with an email address.

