### **Participants**

Participants will complete their first visit with research staff at Penn State Hershey or signed exercise sites (60 minutes baseline visit plus 30 minute DXA scan, if applicable).

Prior to the baseline visit, research staff will send participants the following questionnaires, to be completed at home and brought with them to the baseline assessment: sociodemographic and past medical history, fear of falling, falls history (BRFSS), self-reported health, PROMIS 29: depression, anxiety and physical function, fatigue, pain, sleep disturbance, ability to participate in social roles and activities, brief loneliness questionnaire, physical activity, social domain (caregiver), and assistive devices. These surveys should take approximately 20 minutes to complete.

Research staff will review the informed consent document and the liability waiver with individual. Before enrolling the individual (signing the informed consent and liability waiver), a research staff will take the individual's blood pressure and heart rate to screen for eligibility.

- If blood pressure is  $\geq 180$  systolic OR  $\geq 110$  diastolic OR heart rate is  $\geq 120$  bpm, research staff will suggest the individual to see a PCP to control their blood pressure or heart rate, and if they would like to still participate in our study they would have to receive PCP permission before re-screening for eligibility.
- If blood pressure is between 160 to 179 systolic OR 100 to 109 diastolic AND heart rate is  $<120$  bpm, research staff will provide critical value letter to individual and suggest him/her to see a PCP about their high blood pressure, but they will still be enrolled into the study.

If the individual is eligible, based on their blood pressure or heart rate results (above), a research staff will ask if they have any questions about the consent and liability waiver, and if they agree, both the research staff and participant will sign. The participant will be provided with a copy of the signed consent liability waiver for their records.

Research staff will take the participant's baseline measurements: (1) height and weight, (2) blood pressure and heart rate, (3) 30 second chair stand test, 30 second bicep curl test. Research staff will also review participant's medications.

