### **7.2.6.3. Randomization**

Once eligible participants who sign the informed consent and completed the baseline questions, research staff at each site will randomize the participant into one of two groups (control, enhanced usual care; or intervention groups, enhanced usual care plus coached exercise program) in a one-to-one ratio. Stratification factors for randomization will be study site location (1=Penn State, 2=University of Pittsburgh, 3=Temple University), gender (0=female, 1=male), and bisphosphonate and other potent medication use (0=never, 1=ever). The research staff will conduct the randomization during the baseline visit through REDCap.

Participants randomized to the intervention group will also receive an introductory letter from their exercise coach with picture/name and details on a forthcoming phone call.

Group leaders, community members, and Spanish Speaking Interview members will not be randomized.

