### **18.3 Subject Enrollment**

The lead investigative team meets on a weekly basis and one of the topics discussed will be recruitment. The core project manager and Site PIs will provide updates to the group on each site’s recruitment

status. The core project manager will also check in weekly with the site project managers. In addition, we will have an Engagement committee who will be meeting regularly to discuss recruitment and retention milestones and barriers.

Randomization will be conducted through REDCap. The randomization scheme is stratified by site (Penn State/ University of Pittsburgh/ Temple University), gender (male/female), and bisphosphonate use (ever/never). [name] will work with the study statistician to create the randomization list, based on expected rates of recruitment of each strata from each study site.

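### The pre-specified primary covariates in 8.3 leave out baseline falls history, fear of falling and chair stand, all of which the trial collects; the cost is small and the remedy is nearly free

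*Combined protocol and SAP*

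**What the plan says.** The primary adjustment set is stated in 8.3: "the covariates of medical center, age, sex, race and ethnicity, smoking status, education, and anti-osteoporotic medication use included in the primary set of analyses". The list is fixed in advance. No regression model is named for it. A two-tailed log-rank test appears in the sample-size text of 8.2 and in the sample-size paragraph of 8.3.

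Section 8.3 first says that "the two randomized groups will be compared qualitatively on important demographic and other baseline variables to ensure successful randomization". It then adds a rule for anything outside the list: "If it is determined that the groups, by chance, are significantly different on other covariates, then we will include those covariates in secondary analyses".

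Three fall-risk measures are taken at baseline and are not on the list:

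- **Falls history.** Section 1.3 measures falls "using two questions from the Behavioral Risk Factor Surveillance System (BRFSS) at baseline".
- **Fear of falling.** Section 1.3 credits the seven-item FES-I with high test-retest "reliability and is strongly associated with future falls and depression". Section 7.2.6 (Participants) puts it in the pre-visit questionnaires, which include "fear of falling, falls history (BRFSS), self-reported health".
- **Chair stand.** The 30-second test is scheduled at baseline in 1.3, in the 7.2.1 flowchart and in 7.2.6.

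The medication stratum is "bisphosphonate and other potent medication use (0=never, 1=ever" in 7.2.6.3 and "bisphosphonate use (ever/never" in 18.3. The covariate in 8.3 has its own label and no time point, while 1.3 records past osteoporosis medication at baseline and a current medication list at 36 months.

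**The concern.** Once an analysis adjusts at all, the useful covariates are those that predict the outcome. For serious fall-related injury one would look first to previous falls, fear of falling and leg strength. The plan has all three in hand before randomisation and uses none of them, but includes smoking and education without giving a reason. At stake are some precision and protection against an unlucky imbalance in the main risk factors.

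The rule for further covariates is a separate weakness. In a properly randomised trial every baseline difference is a chance difference, as the sentence itself says. A significance test on such differences therefore picks variables by luck, and a variable can be picked without being prognostic. This affects which secondary adjusted results appear.

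**Working it through.** **1. The plan's own power.** Inputs: 13% against 7% at 36 months (1.1, and the table in 8.3), 960 completers (8.3), 1:1 allocation (7.2.6.3) giving 480 per arm, two-sided 5% (8.3).

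- Two proportions: null SE = √(2 × 0.10 × 0.90/480) = 0.01936; alternative SE = √((0.13 × 0.87 + 0.07 × 0.93)/480) = 0.01927; z = (0.06 − 1.96 × 0.01936)/0.01927 = 1.14; power 87.4%.
- Freedman log-rank: events = 480 × 0.13 + 480 × 0.07 = 96; HR = ln 0.93/ln 0.87 = 0.521; z = √96 × 0.479/1.521 − 1.96 = 1.13; power 87.0%.

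The stated 87% reproduces. Neither calculation uses covariates.

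**2. Power from adding prior falls.** Assumed: a yes/no covariate with prevalence q of 30% to 50% and hazard ratio g of 1.5 to 3. Solve (1 − q)(1 − e^(−Hc)) + q(1 − e^(−Hcg)) for a risk of 0.13 with c = 1, then for 0.07 to get the conditional treatment hazard ratio c. Schoenfeld power is Φ(√96/2 × |ln c| − 1.96). Unadjusted, with c = 0.521, it is 89.1%.

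| q | g | c | Power | Gain (points) |
|---|---|---|---|---|
| 30% | 1.5 | 0.520 | 89.2% | 0.1 |
| 30% | 2 | 0.519 | 89.5% | 0.4 |
| 30% | 3 | 0.515 | 90.1% | 1.0 |
| 50% | 1.5 | 0.520 | 89.2% | 0.1 |
| 50% | 2 | 0.519 | 89.5% | 0.3 |
| 50% | 3 | 0.517 | 89.9% | 0.8 |

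**3. A stronger combined score.** Cox simulations at this sample size (3,000 trials per setting) gave gains of 0.6, 2.2 and 4.1 points for a prognostic score with log-hazard SD of 0.5, 0.8 and 1.0. The formula in step 2, averaged over a normal score with the same SDs, gives 0.8, 2.3 and 3.7. For scale, prior falls at 50% prevalence has SD 0.5 × ln g, which is 0.35 for g = 2 and 0.55 for g = 3. The larger gains therefore need the three measures together to predict well.

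**4. Chance imbalance.** Assume q = 50%. The SD of the difference between arms is √(2 × 0.25/480) = 3.2 points, so 1.96 SD is 6.3 points. With 53.16% prior fallers in one arm and 46.84% in the other, the hazard ratio shifts by the ratio of mean hazards:

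- g = 2: (1 + 0.5316)/(1 + 0.4684) = 1.043
- g = 3: (1 + 2 × 0.5316)/(1 + 2 × 0.4684) = 1.065

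Applied to the planned 0.521, this gives 0.521/1.043 = 0.50 to 0.521 × 1.043 = 0.54 for g = 2, and 0.49 to 0.55 for g = 3, depending on the direction. An imbalance at least this large arises in about 1 trial in 20. At one SD the shifts are 1.516/1.484 = 1.022 and 2.032/1.968 = 1.033.

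**5. The significance rule.** Section 8.3 gives neither a test level nor a list of candidates. If k independent variables are tested at 5%, the chance of at least one significant difference is 1 − 0.95^k: 23% for k = 5, 40% for 10, 54% for 15 and 64% for 20. Correlated questionnaires would lower these figures.

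**The case against.** The strongest defence is that nothing here threatens validity. Omitting a prognostic covariate neither biases a randomised comparison in expectation nor invalidates its test. The planned analysis already adjusts for age, sex, center and medication, and the gains above compare adjusted with unadjusted analyses. If falls history overlaps with age and sex, the increment over the planned model is smaller, and it has not been computed. The protocol's remark on the FES-I concerns falls, not adjudicated serious injuries, and 1.3 presents fear of falling as a hypothesised mediator. All of this stands and keeps the point modest. The mediator remark does not rule out the baseline value, which precedes randomisation.

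A reader might also infer three stronger things that the documents do not support:

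- **That significance testing decides the primary model.** It does not: 8.3 sends those covariates to secondary analyses only, and describes the first baseline comparison as qualitative.
- **That there are two competing primary p-values.** The log-rank test is named only where the sample size is worked out, and sizing on it while analysing with covariates is ordinary. What is missing is the name of the adjusted model.
- **That the analysis drops or replaces a randomisation stratum.** Center, sex and medication use are all on the list, and the label in 8.3 is compatible with the stratum in 7.2.6.3. The three wordings and the absent time point need reconciling, no more.

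**Conclusion.** The point holds as a worthwhile, low-cost improvement and not as a flaw in the primary inference. The primary covariates are pre-specified, but they leave out collected baseline predictors of falling. The loss is about 0.1 to 1 point of power for prior falls alone and perhaps 2 to 4 points for a strong combined score. A 6-point chance imbalance in prior falls would go uncorrected and shift the hazard ratio by about 4% to 7%. These sizes rest on assumed prevalence and prognostic strength. That the three measures are collected and not listed is plain from the text.

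The significance-based rule is poor practice, but its reach ends at the secondary analyses. How often it would trigger cannot be stated without assuming the number of variables, their independence and the test level.

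**What to change.** Before outcomes are compared by arm, amend 8.3 as follows:

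- Name one primary analysis of time to first SFRI, for example a Cox model. Add baseline BRFSS falls history, baseline FES-I score and baseline chair-stand count to the covariates already listed. The demographic covariates may stay; moving them out would be a matter of preference.
- State that the medication covariate is the baseline ever/never stratum exactly as coded for randomisation, and align the wording of 7.2.6.3, 8.3 and 18.3.
- Keep the unadjusted log-rank test as a supportive analysis.
- Replace the significance rule with secondary covariates named in advance on prognostic grounds. The baseline table can stay descriptive.

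The cost is plan wording, a few more model terms against about 96 expected events, and simple imputation for the few participants likely to lack a baseline item. No new data are needed.
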